9.2.1.1. Suspected Unexpected Serious Adverse Reactions

Suspected unexpected serious adverse reactions (SUSARs) are serious events that are not listed in the galcanezumab IB or the erenumab US package insert (USPI) and that the investigator identifies as related to study treatment or procedure. United States 21 CFR 312.32 and European Union Clinical Trial Directive 2001/20/EC and the associated detailed guidances or national regulatory requirements in participating countries require the reporting of SUSARs. Lilly has procedures that will be followed for the identification, recording, and expedited reporting of SUSARs that are consistent with global regulations and the associated detailed guidances.

9.2.2. Complaint Handling

Lilly collects product complaints on study treatment and drug delivery systems used in clinical studies to ensure the safety of study participants, monitor quality, and to facilitate process and product improvements.

Patients will be instructed to contact the investigator as soon as possible if he or she has a complaint or problem with the study treatment (galcanezumab or erenumab) or device (AI or WMC) so that the situation can be assessed.

9.3. Treatment of Overdose

Refer to the IB for galcanezumab and the Product Label for erenumab.

9.4. Safety

9.4.1. Vital Signs

For each patient, vital signs measurements should be conducted according to the Schedule of Activities (Section 2).

Any clinically significant findings from vital signs measurement that result in a diagnosis and that occur after the patient receives the first dose of study treatment should be reported to Lilly or its designee as an AE via eCRF.

9.4.2. Laboratory Tests

For each patient, the local urine pregnancy test should be conducted according to the Schedule of Activities (Section 2).

9.4.3. Immunogenicity Assessments

Not applicable.

9.4.4. Safety Monitoring

Lilly will periodically review evolving aggregate safety data within the study by appropriate methods.

9.4.4.1. Hepatic Safety Monitoring

Not applicable.

9.5. Pharmacokinetics

Not applicable.

9.6. Pharmacodynamics

Not applicable.

9.7. Genetics

Not applicable.

9.8. Biomarkers

Not applicable.

9.9. Health Economics

Health Economics and Medical Resource Utilization parameters are not evaluated in this study.

10. Statistical Considerations

10.1. Sample Size Determination

Assuming within-group mean difference in CTT is about 4.2 hours with standard deviation of approximately 8, a sample of 30 patients in each treatment group will provide 80% power to detect the difference within the treatment group. The total sample size for the study would be 60.

Assuming 20% screen failure rate, approximately 75 patients may be screened to enroll 60 patients into the study. Eligible patients will be randomized in a 1:1 ratio to galcanezumab or erenumab to have about 30 patients in each treatment group.

10.2. Populations for Analyses

For purposes of analysis, the intent-to-treat (ITT) population will be used. The ITT population includes all patients who are randomized and received study treatment. Other populations may be explored if appropriate, such as the ITT population excluding patients taking prohibited medications that are known to have an effect on GI motility or the WMC test.

10.3. Statistical Analyses

10.3.1. General Statistical Considerations

Statistical analysis of this study will be the responsibility of Lilly or its designee. Details of statistical analysis methods will be described in the statistical analysis plan (SAP).

Unless otherwise specified, analyses will be conducted on the ITT population, which will include all patients who are randomized and receive at least 1 dose of study treatment. Patients in the ITT population will be analyzed according to the treatment group to which they are randomized. When change from baseline is assessed, the patient will be included in the analysis only if the patient has baseline and postbaseline measurements.

Investigative sites with fewer than 4 randomized patients per treatment group will be pooled for statistical analysis purposes.

All tests of within-group and between-group comparisons will be conducted at a 2-sided alpha level of 0.05, unless otherwise stated.

Any change to the data analysis methods described in the protocol will require an amendment ONLY if it changes a principal feature of the protocol. Any other change to the data analysis methods described in the protocol, and the justification for making the change, will be described in the SAP or the clinical study report (CSR). Additional exploratory analyses of the data will be conducted as deemed appropriate.

10.3.2. Treatment Group Comparability

10.3.2.1. Patient Disposition

The number and percentage of ITT patients who complete the study or discontinue early will be summarized for both treatment groups. A detailed description of patient disposition will be provided at the end of the study.

Patient allocation by investigative site will be summarized for ITT population. Patient allocation by investigative site will also be listed.

10.3.2.2. Patient Characteristics

The following patient characteristics at baseline will be summarized by treatment group for ITT population:

- demographics (age, gender, ethnic origin, height, weight, body mass index)
- medical history and pre-existing condition
- total gut and segmental transit times, and
- GI symptom rating scale, SBM frequency, and Bristol stool form scale.

10.3.2.3. Concomitant Therapy

The proportion of patients who received concomitant medication will be summarized for all ITT patients.

10.3.2.4. Treatment Compliance

Not applicable.

10.3.3. Efficacy Analyses

10.3.3.1. Primary Analyses

The primary objective is to assess changes in CTT between pre- and post-drug administration within each treatment group. The primary measure is the mean change from baseline in the CTT 2 weeks after drug administration within each treatment group.

The primary analysis will be performed using an analysis of covariance (ANCOVA) model. The analysis will include the categorical effects of treatment and all randomization stratification factors (site, baseline migraine frequency, and BMI category; see Section 7.2), as well as the continuous baseline CTT. Least squares mean change from baseline in each treatment group will be tested to detect any change in CTT between pre- and post-drug administration.

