3.1. Study Rationale

Differences have been observed between reported frequencies of constipation in clinical trials and postmarketing adverse event (AE) reporting among calcitonin gene-related peptide (CGRP) antagonists. In particular, these differences have been observed between CGRP monoclonal antibodies (mAb) that target the ligand (galcanezumab, fremanezumab) or the receptor (erenumab) for the prevention of migraine (Stauffer et al. 2018b; Ashina et al. 2019; Robbins 2019; Silberstein et al. 2019; Aimovig package insert, 2020). Preclinical animal studies suggest that the different mechanisms of action of these agents may contribute to the different frequencies of constipation (Hargreaves and Olesen 2019). The purpose of Study I5Q-MC-CGBC (CGBC) is to measure gastrointestinal (GI) transit time in adult patients with migraine who have been initiated on preventive treatment with a CGRP antagonist (galcanezumab or erenumab), and explore whether there is a mechanistic difference that contributes to GI AEs in humans.

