One possible explanation for the differences between reported frequencies of constipation in Phase 2 and 3 clinical trials, postmarketing clinician observation, and postmarketing AE reporting for monoclonal antibodies that act at the CGRP ligand versus the CGRP receptor could involve the effects of CGRP at the AMY1 receptor (Hay et al. 2018; Stauffer et al. 2018b; Aimovig package insert, 2020; Ashina et al. 2019; Hargreaves and Olesen 2019; Robbins 2019; Silberstein et al. 2019). By blocking the CGRP receptor, the CGRP receptor antagonist (erenumab) would decrease the motility-enhancing characteristics of CGRP while maintaining, or perhaps increasing, the GI motility-slowing effects via AMY1 receptor activation. Alternatively, the CGRP antagonist acting at the ligand would inhibit the motility-enhancing and motility-slowing effects of CGRP at the CGRP and AMY1 receptors, respectively, with the net effect being little to no change in GI transit time. This hypothesis will be studied in this clinical trial.

Abbreviations: AMY1 = amylin 1; CGRP = calcitonin gene-related peptide.

Figure CGBC.3.1. Mechanism of action of CGRP monoclonal antibodies.

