
Secondary Objectives To evaluate transit time of the following segments of the gastrointestinal (GI) tract 1 week prior to and 2 weeks after administration of galcanezumab or erenumab:
 
 • whole gut • gastric emptying • small bowel • combined small and large bowel. 	Change from baseline in GI transit time in each of the following segments after administration of galcanezumab or erenumab within each treatment group at the end of Week 2: 
 • Whole gut transit time (WGTT), in hours • Gastric emptying time (GET), in hours • Small bowel transit time (SBTT), in hours • Combined small and large bowel transit time (SLBTT), in hours.
To evaluate the frequency of contractions, motility index, and area under the pressure curve (AUC) by quartile in the colon to assess for correlation with CTT results.	Changes in pressure parameters from baseline: 
 • Contraction Freq/Min • Motility Index = $\ln(\# \text{ of contractions} \times \sum \text{pressure amplitudes} + 1)$ • Area under the Pressure Curve.
To evaluate number of weekly spontaneous bowel movements (un-aided by laxatives, enemas, or suppositories) prior to and after administration of galcanezumab or erenumab.	Change from baseline in number of weekly spontaneous bowel movements after administration of galcanezumab or erenumab within each treatment group at Weeks 2 and 4.
To evaluate GI symptom rating scale (GSRS) prior to and after administration of galcanezumab or erenumab.	Change from baseline in GSRS after administration of galcanezumab or erenumab within each treatment group at Weeks 2 and 4.
To evaluate the Bristol stool form scale (BSFS) prior to and after administration of galcanezumab or erenumab.	Change from baseline in BSFS after administration of galcanezumab or erenumab within each treatment group at Weeks 2 and 4.

Tertiary/Exploratory Objectives To evaluate the transit time between galcanezumab and erenumab for
 
 • whole gut • gastric emptying • small bowel • colon • combined small and large bowel. 	Change from baseline in transit time after administration of galcanezumab or erenumab between treatment groups at the end of Week 2 for 
 • WGTT, in hours • GET, in hours • SBTT, in hours • CTT, in hours • combined SLBTT, in hours.

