**Figure CGBC.5.1. Illustration of study design for Clinical Protocol I5Q-MC-CGBC.**

### 5.2. Determination of Sample Size

Assuming that the within-group mean difference in CTT is approximately 4.2 hours with a standard deviation of approximately 8, a sample of 30 patients in each treatment group will

provide 80% power to detect the difference within the treatment group. The total sample size for the study is 60 patients.

Assuming a 20% screen failure rate, approximately 75 patients may be screened to enroll 60 patients in the study. Eligible patients will be randomized in a 1:1 ratio to galcanezumab or erenumab to enroll approximately 30 patients in each treatment group.

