## 6.10. Efficacy Analyses

### 6.10.1. Primary Outcome and Methodology

The primary analysis will evaluate the change from baseline in CTT (hours) after administration of an initial loading dose of galcanezumab 240 mg or erenumab 140 mg at the end of Week 2.

The primary analysis will be performed using an ANCOVA model including the categorical effects of treatment, pooled investigative site, BMI category ( $<30\text{kg/m}^2$ ,  $\geq 30\text{kg/m}^2$ ), and baseline migraine frequency ( $<8$  migraine headache days,  $\geq 8$  migraine headache days), as well as the continuous baseline CTT (hours).

The primary endpoint of this study for galcanezumab 240 mg and erenumab 140 mg will be estimated as the least squares (LS) mean change from baseline to Week 2 from the ANCOVA model. The type I error rate for the study will be controlled at a 2-sided 0.05 level.

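### Does a trial whose hypothesis is a difference between two drugs need to change because its primary tests are before-after changes within each arm?

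*Protocol*

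**What the plan says.** Protocol 3.2 sets out the mechanism. Blocking the receptor (erenumab) should remove a motility-enhancing effect and leave the slowing pathway in place. Binding the ligand (galcanezumab) should remove both effects, "with the net effect being little to no change in GI transit time. This hypothesis will be studied in this clinical trial". Protocol 3.1 puts the aim more cautiously: to "explore whether there is a mechanistic difference that contributes to GI AEs in humans".

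The primary objective is about each drug separately. Protocol 10.3.3.1 says: "The primary measure is the mean change from baseline in the CTT 2 weeks after drug administration within each treatment group". SAP 6.10.1 adds that the endpoint for each drug "will be estimated as the least squares (LS) mean change from baseline to Week 2 from the ANCOVA model". The sample size follows the same logic. SAP 5.2 begins "Assuming that the within-group mean difference in CTT is approximately 4.2 hours with a standard deviation of approximately 8", and Protocol 10.1 concludes that "a sample of 30 patients in each treatment group will provide 80% power to detect the difference within the treatment group". The only CTT sensitivity analysis, the signed rank test in SAP 6.10.3, is also within arm.

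The comparison between drugs is ranked lower but is present. The tertiary/exploratory part of Table CGBC.4.1 (Protocol Section 4) lists "Change from baseline in transit time after administration of galcanezumab or erenumab between treatment groups at the end of Week 2 for" five transit times, one of them CTT. SAP 6.10.2 then says that the LS mean changes in CTT for the two drugs will be compared within the primary ANCOVA, to look for a difference between groups.

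**The concern.** The hypothesis predicts slowing in one arm and nothing much in the other. The headline output will be two separate p-values, and the predicted pattern (erenumab significant, galcanezumab not) is the one most easily over-read, for three reasons.

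- One significant test and one non-significant test do not show that the two drugs differ. That pattern can arise by chance when both drugs have the same effect.
- A non-significant test does not show that nothing changed. With 30 patients the interval may still include an effect as large as the one the trial was sized to find.
- Both arms are active. A change from the first capsule to the second may reflect the drug or anything else that shifts between visits. Only the randomised contrast removes a shift common to both arms.

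The plan gives power for the within-arm tests only. It does not state the expected precision of the contrast, or say in so many words that a claim of a drug difference must rest on it. If the within-arm p-values were set side by side and read as a comparison, the trial could support a mechanistic claim that it had not tested.

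**Working it through.** **Inputs.** 30 patients per arm, 4.2 h mean change, SD 8 (Protocol 10.1, SAP 5.2); two-sided alpha 0.05 (Protocol 10.3.1, SAP 6.5). The SD is read as the SD of the change, because the stated power then follows without a further correlation assumption.

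**1. The plan's own figure (one-sample t-test on the change).**
- SE = 8/√30 = 1.461 h; noncentrality = 4.2/1.461 = 2.876; 29 df; critical t = 2.045.
- Power = 79.4%, which reproduces the stated 80%.
- 95% CI half-width = 2.045 × 1.461 = 2.99 h.

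**2. The between-drug contrast on the same inputs (two-sample t-test, unadjusted).**
- SE = 8 × √(2/30) = 2.066 h; 58 df; critical t = 2.002.
- 95% CI half-width = 2.002 × 2.066 = 4.13 h.
- Noncentrality for an assumed 4.2 h difference (4.2 h with erenumab, 0 h with galcanezumab) = 4.2/2.066 = 2.033, giving power 51.6%.
- 80% power for 4.2 h would take about 58 per arm, or 116 in total against the planned 60.

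**3. How often equal drugs give discordant p-values.** With independent unadjusted tests of power p, exactly one arm is significant with probability 2p(1 − p). The predicted pattern (erenumab significant, galcanezumab not) has probability p(1 − p), half of that.

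| Equal true change in both arms | p | Exactly one significant | Erenumab only |
|---|---|---|---|
| 3 h | 0.510 | 50% | 25% |
| 4.2 h | 0.794 | 33% | 16% |

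The planned ANCOVA adjusts for baseline, pooled site, BMI and migraine frequency, and lowers these figures. Simulations of that model with equal true change, under assumed baseline-to-Week 2 correlations of 0.2 to 0.8 and 3 or 6 pooled sites, gave exactly one significant arm in 15–29% of trials at 4.2 h and 35–45% at 3 h. The between-drug test rejected in about 5%, as it should.

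**4. Reading non-significance as no change.** A result just short of significance has an upper limit of about twice the half-width: 2 × 2.99 = 5.97 h, above the 4.2 h design effect. That is the extreme case. If the true change is zero, a non-significant result with an upper limit above 4.2 h occurs about 18% of the time (unadjusted, simulated).

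**5. What the plan asks analysts to do.** The within-arm tests are assigned to detecting a change from before to after dosing (Protocol 10.3.3.1). The between-group LS mean comparison from the same model is assigned to detecting a difference between drugs (SAP 6.10.2). No passage uses the first to answer the second question. So the discordance rates in step 3 describe a misreading that a careless reader could make. They are not the error rate of any planned test.

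**The case for a change.** The strongest case for a change is that Protocol 3.2 says outright that the trial will study this hypothesis, while the primary test, the power statement and the CTT sensitivity analysis all leave the drug difference aside. Protocol 10.3.3.2 describes a between-group comparison for secondary measures only, and Protocol 10.3.3.3 describes a repeated-measures model that does not fit CTT, which has one post-dose value. Only the SAP specifies the CTT contrast. Fixing the interpretation rule before data are seen would remove discretion at the cost of a few sentences.

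The facts in that argument stand, and so do the figures. Three things keep it from requiring a change.

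- **The contrast is already fixed in advance.** Protocol 10.3.1 leaves analysis details to the SAP, and SAP 6.10.2 supplies the model and the comparison. A statistician asked whether the drugs differ has one prespecified CTT comparison to use.
- **Its rank is an open choice.** The documents call the aim exploratory, so power below 80% for it is not an error, and a stated power or interval width is not normally expected for a tertiary endpoint.
- **A fuller precision statement would rest on guesses.** Only the unadjusted 4.1 h and 52% follow from the plan's inputs. Adjusted figures depend on the correlation between visits, the SD at each visit, the number of pooled sites, the mix of strata and how many capsule readings are missing, and the documents give none of these.

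A related worry is that the capsule readers are stated to be blind to treatment but not to visit, which is the mask that matters for a before-after reading. It does not change the answer. The documents show no reading bias by visit and refer to a Manual of Operations for blinding details. Holding baseline readings for a visit-masked read could also mean that an unusable baseline recording is found late.

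**Conclusion.** No change is needed. The stated power is correct for the test it describes (79.4% against 80%), and the randomised CTT comparison is prespecified in the primary model. Its limited precision follows from treating the drug difference as exploratory: about ±4.1 h and about 52% power for an assumed 4.2 h difference, unadjusted. Those two figures assume 30 evaluable patients per arm and an SD of change of 8 h; missing capsule readings would weaken them, and baseline adjustment may improve them.

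What the plan leaves unsaid is ordinary good practice: report the between-group LS mean difference with its 95% confidence interval beside the within-arm results, rest any statement about a drug difference on it, and do not read a non-significant arm as unchanged. Analysts can do all of this from the planned output. A sentence to that effect in SAP 6.10.2 would be harmless but would change no test, model, estimate or number, and it would not justify a protocol amendment. The point would have held if any passage had drawn a drug difference from the two within-arm tests, or if the randomised contrast had been left out.

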### 6.10.2. Secondary and Tertiary Efficacy Analyses

The LS mean change from baseline to Week 2 in CTT (hours) between galcanezumab 240 mg and erenumab 140 mg will be compared to detect any between-group differences in the primary model described above.

For continuous secondary/tertiary measures with a single postbaseline measurement, analysis will be performed using an ANCOVA model. The analysis will include the categorical effects of treatment and all randomization stratification factors, as well as the continuous baseline value. The LS mean change from baseline in each treatment group will be tested to detect any changes between pre- and post-treatment administration. The LS mean change from baseline in the 2 treatment groups will also be compared to detect any between-group differences.

For continuous efficacy measures with repeated postbaseline measurements, change from baseline will be analyzed using a REML-based MMRM technique. The analysis will include the fixed categorical effects of treatment, pooled investigative site, BMI category ( $<30\text{kg/m}^2$ ,  $\geq 30\text{kg/m}^2$ ), baseline migraine frequency ( $<8$  migraine headache days,  $\geq 8$  migraine headache days), week, and treatment-by-week interaction, as well as the continuous fixed covariates of baseline value and baseline-by-week interaction.

An unstructured covariance structure will be used to model the within-patient errors. The Kenward-Roger (Kenward and Roger 1997) approximation will be used to estimate the denominator degrees of freedom. If the model does not converge, with both the Hessian and the G matrix being positive definite under the default fitting algorithm used by PROC MIXED, the Fisher scoring algorithm will be implemented by specifying the SCORING option in SAS®. If the model still fails to converge, the model will be fit using covariance matrices of the following order specified by a decreasing number of covariance parameters until convergence is met:

- heterogeneous Toeplitz
- heterogeneous first-order autoregressive
- Toeplitz, and
- first-order autoregressive.

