When the unstructured covariance matrix is not utilized, the sandwich estimator (Diggle and Kenward 1994) will be used to estimate the standard errors of the fixed-effects parameters. The sandwich estimator is implemented by specifying the EMPIRICAL option in SAS. When the sandwich estimator is utilized, the Kenward-Roger approximation for denominator degrees of freedom (Kenward and Roger 1997) cannot be used. Instead, the denominator degrees of freedom will be partitioned into between-subject and within-subject portions by the DDFM=BETWITHIN option in SAS. SAS PROC MIXED will be used to perform the analysis.

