### **6.10.3. Sensitivity Analyses**

The primary analysis assumes that data are normally distributed. To assess the impact of the normality assumption, a nonparametric sensitivity analysis of the primary endpoint will be produced using the Wilcoxon signed rank test (Wilcoxon 1945) to compare the change from baseline within each treatment group.

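### The ordinary ANCOVA standard error for each arm's mean change in CTT ignores sampling variation in the baseline mean, so the primary within-arm tests can exceed their nominal 5%

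*Protocol*

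**What the plan says.** Protocol 10.3.3.1 names the target: "The primary measure is the mean change from baseline in the CTT 2 weeks after drug administration within each treatment group". The same section, and SAP 6.10.1, estimate it as each arm's LS mean change from a single ANCOVA with treatment, site (pooled in the SAP), BMI category, baseline migraine frequency and continuous baseline CTT. The protocol section then sets the test: "Least squares mean change from baseline in each treatment group will be tested to detect any change in CTT between pre- and post-drug administration". SAP 6.10.1 adds: "The type I error rate for the study will be controlled at a 2-sided 0.05 level". Protocol 10.1 powers the study on a within-group change of 4.2 h with SD 8, and says "a sample of 30 patients in each treatment group will provide 80% power to detect the difference within the treatment group".

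Neither document says whether the within-arm inference is conditional on the observed baselines, or at which covariate margins the LS mean is taken. The SE and degrees-of-freedom options in SAP 6.10.2 (Kenward-Roger; "The sandwich estimator is implemented by specifying the EMPIRICAL option in SAS") belong to the repeated-measures model. SAP 6.10.3 plans a within-arm check that does not use the ANCOVA SE: "a nonparametric sensitivity analysis of the primary endpoint will be produced using the Wilcoxon signed rank test". Its stated purpose is to examine normality.

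**The concern.** ANCOVA is normally used to compare arms. Both LS means are then evaluated at the same baseline mean, and any error in that mean cancels in the difference. Here the primary tests are on each arm separately, so nothing cancels. If change in CTT depends on baseline CTT, the LS mean moves with the baseline mean of the patients who happened to enrol, and the usual SE does not count that movement.

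The two within-arm tests are the trial's primary result. If the SE is too small for the stated target, p-values are too small and intervals too narrow, and the commitment to a 0.05 error rate need not hold even for one test taken alone. Multiplicity across the two arms is a separate matter and is not counted here.

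**Working it through.** **The plan's own figure.** Paired t-test, n = 30, change 4.2 h, SD 8: SE = 8/√30 = 1.461 h, noncentrality 4.2/1.461 = 2.88, 29 df, 2-sided 0.05. Power is 79.4%, which agrees with the stated 80%. The power basis is therefore an unconditional mean change.

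**Inputs.** From the documents: n = 30 per arm, N = 60, SD of change 8, alpha 0.05 2-sided. Assumed, because neither document gives them: the pre/post correlation ρ and the ratio k = post SD/pre SD.

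**Formula.** Let σ be the pre-dose SD.
- Slope of change on baseline: b = ρk − 1.
- Residual variance: σ²k²(1 − ρ²).
- Model variance of an arm's LS mean: about σ²k²(1 − ρ²)/n.
- Omitted term: b²σ²/N, with N = 2n.
- True/model variance: R = 1 + (ρk − 1)²/[2k²(1 − ρ²)].
- Size: 2·P(t > t_crit/√R).

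R does not depend on n, so more patients would not remove the problem.

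**Worked case: k = 1, ρ = 0.5.** An SD of change of 8 gives σ = 8/√(2 × 0.5) = 8. Then b = −0.5, residual variance = 64 × 0.75 = 48, and model variance = 48/30 = 1.60. The omitted term is 0.25 × 64/60 = 0.267. So R = 1.867/1.60 = 1.167 and the size is 6.9%.

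**Grid.** Formula sizes use a model with treatment and baseline only (57 df). Simulated sizes use the planned model with BMI, migraine and pooled-site terms. The number of pooled sites is not given, so values from 2 to 7 were tried; a range shows the spread over separate runs.

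| k | ρ | R | Size, formula | Size, simulated planned model |
|---|---|---|---|---|
| 1 | 0.2 | 1.333 | 8.8% | 8.3–8.8% |
| 1 | 0.5 | 1.167 | 6.9% | 6.7–7.3% |
| 1 | 0.8 | 1.056 | 5.6% | 5.7–5.8% |
| 1 | 0.9 | 1.026 | 5.3% | 5.0–5.3% |
| 0.8 | 0.2 | 1.574 | 11.6% | 10.5–11.0% |
| 0.8 | 0.5 | 1.375 | 9.3% | 8.8% |
| 0.8 | 0.8 | 1.281 | 8.2% | 7.9% |
| 1.25 | 0.2 | 1.188 | 7.1% | 6.7% |
| 1.25 | 0.5 | 1.060 | 5.7% | 5.3% |
| 1.25 | 0.8 | 1.000 | 5.0% | 4.7–5.1% |

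With k = 1, the mean model SE against the actual SD of the LS mean was 1.142 against 1.321, 1.277 against 1.384, and 1.399 against 1.444 h at ρ = 0.2, 0.5 and 0.8.

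**Which rows are plausible.** With k = 1 and SD of change 8, the raw CTT SD is 8/√(2(1 − ρ)): 6.3, 8.0, 12.6 and 17.9 h at ρ = 0.2, 0.5, 0.8 and 0.9. A wide raw spread would put the size near 5.3–5.6%.

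**Checks on remedies.**
- Adding b²s_b²/N to the squared SE (b the estimated slope, s_b² the sample variance of baseline CTT) gave 4.5–5.0% under the planned factors.
- The paired t-test gave 4.7–5.2%. The between-arm test gave 4.9–5.2% with no correction.
- An HC3 sandwich SE still gave 11.1% at ρ = 0.2, k = 0.8 in the two-term model, and 8.7% there with strata and four sites.
- Margins matter. With an assumed 4 h BMI effect on change, 35% of patients at BMI ≥30 and k = 1, the baseline correction gave 5.1/5.0/5.1% at observed margins but 7.4/6.8/6.7% at equal margins (ρ = 0.2/0.5/0.8).

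**The case against.** The strongest reply is that the plan defines the estimate as the ANCOVA LS mean and that, conditional on the observed baselines, the ordinary test holds its 5%. The conditional statement is correct. But it concerns change at the observed baseline mean, whereas Protocol 10.3.3.1 names the mean change in each group, and Protocol 10.1 powers an unconditional change. Neither document announces the narrower hypothesis.

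It is also fair that the large values need unfavourable inputs. The top corner combines ρ = 0.2 with a 36% fall in CTT variance after dosing (1 − 0.8² = 0.36), and nothing in the documents leads one to expect that.

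The Wilcoxon test is unaffected and gives some protection. It is offered only as a normality check, though, so a disagreement with the ANCOVA could be put down to the wrong cause.

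A reader might infer four stronger things that the documents do not support:
- That the true size is 11.6%. That figure is the two-term formula at one corner of an assumed grid; under the planned model the same corner is about 11%.
- That the failure to name an SE method is the defect. An ordinary ANCOVA implies the model-based SE, and naming a plain sandwich SE would not repair it.
- That the between-arm comparison is compromised. The omitted term cancels there.
- That the stated 80% power is wrong. It reproduces.

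**Conclusion.** The point holds for the within-arm tests of population mean change. With 30 per arm and equal pre/post SDs, a nominal 5% test has size of about 8.5% at ρ = 0.2, 7% at 0.5, 5.7% at 0.8 and 5.0–5.3% at 0.9. Over ρ 0.2–0.8 and SD ratio 0.8–1.25 it runs from about 5%, meaning no inflation, to about 11%. These limits are assumptions, and values outside them can give more: the formula gives 13.9% at ρ = 0 and ratio 0.8. The error-control statement in SAP 6.10.1 therefore need not hold for these tests, even one at a time. The inflation could be negligible, but the documents give nothing from which to tell.

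The same reasoning applies to the single-postbaseline ANCOVA tests in SAP 6.10.2, where "The LS mean change from baseline in each treatment group will be tested to detect any changes between pre- and post-treatment administration"; no size was computed for those endpoints. The repeated-measures tests were not examined.

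**What to change.** In SAP 6.10.1, keep the ANCOVA and state that, for the within-arm tests and intervals, each LS mean is evaluated at the observed covariate margins. Add the sampling variance of the covariate means to its squared SE: at least b² × s_b²/N for baseline CTT, with N the number of patients analysed. Apply the same rule to the within-arm, single-postbaseline ANCOVA tests in SAP 6.10.2. Leave the between-arm contrast as it is.

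Alternatively, report a paired t-test of change in each arm. It matches the power basis (79.4%) but gives up covariate adjustment, and replacing the prespecified test is more likely to count as a change to a principal feature.

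The cost is a sentence or two and a few lines of code, with no new data. Under Protocol 10.3.1 the sponsor decides whether an amendment is needed or a description in the SAP is enough. With equal SDs and ρ = 0.2–0.8, the corrected SE is about 15% to 3% larger (√1.333 = 1.155; √1.056 = 1.028). Power for 4.2 h is 87.6%, 84.4% and 81.2% at ρ = 0.2, 0.5 and 0.8, still meeting the stated 80%. The paired t-test SE of 1.46 h is about 28% to 4% above the uncorrected model SE over the same range.
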